6.3.2.6. Olsen characterization of AK lesions

Definition

The lesions in the identified treatment area will be classified based on Olsen characterization. It consists in the following grades:

- *Olsen Grade I*: Early AK appear as single or few, differently sized, from 0.1-0.3-5.0 cm, in size, rough, blurred, less visible than palpable (palpable on the roughness of the surface), red, rough spots or very flat, non-edged plaques which reach into the reddish colour and are easier to feel than to see;
- *Olsen grade II*: describes advanced AK as clearly visible and palpable, flat, and irregularly raised, with sharp or blurred boundaries, red, rough keratinized surface. If the surface is more strongly keratinized, the AK can also be white, yellow, or light brown. After scratching effects (frequently), a black or blue-black shade may appear (older bleeding);
- *Olsen grade III*: denotes "late" AK that have existed for a longer period of time and are firmly anchored on the lower surface, with an irregular, humpy surface, also wart-like and of different colours (white, brown, black). When the horn deposits are removed, an erosive subsurface is formed.

Olsen characterization (whose outcome will be reported in "AK LESION COUNT AND OLSEN GRADING" eCRF pages) will be evaluated for each patient at Baseline Visit and at Final Visit.

Therefore, in this analysis, the following groups will be considered:

- Olsen I: patients with all lesions graded as Olsen I;
- Olsen II: patients with all lesions graded as Olsen II;
- Olsen III: patients with all lesions graded as Olsen III;
- Olsen I/II: patients with some lesions graded as Olsen I and some lesions graded as Olsen II;

	
Statistical Analysis Plan

	Sponsor: ALMIRALL, S.A.
	Protocol number: M-14789-42

- Olsen I/III: patients with some lesions graded as Olsen I and some lesions graded as Olsen III;
- Olsen II/III: patients with some lesions graded as Olsen II and some lesions graded as Olsen III;
- Olsen I/II/III: patients with some lesions graded as Olsen I, some lesions graded as Olsen II and some lesions graded as Olsen III;
- Complete clearance (Only for Final Visit): patients who performed Olsen Grade evaluation (i.e., patient who answered “Was OLSEN Grading performed? = Yes” in AK LESION COUNT AND OLSEN GRADING eCRF Page) and reported no lesions or patients who did not perform Olsen Grade evaluation because he/she specified no lesions observed (specified in AK LESION COUNT AND OLSEN GRADING eCRF Page);
- Missing: patients with AK lesions who did not perform Olsen Grade evaluation for at least one of them.

Analysis methodology

The number and percentages of patients who performed the AK lesions Olsen Grading at each timepoint (i.e., Baseline Visit and Final Visit) will be reported.

The proportions of patients with lesions classified as described above at Baseline and at Final Visit will be provided with the corresponding 95% CI calculated for the multinomial proportion. In case the lower limit of CI will be negative due to small frequency of the category, 0 will be imputed as lower limit.

Furthermore, a shift table Baseline vs Final Visit with frequency distribution will be produced.

Data handling rules

No missing imputation will be performed.

Sensitivity of secondary analysis

Not applicable.

6.3.2.7. LC-OCT of clinical and subclinical lesions

Definition

Line-field Confocal Optical Coherence Tomography (LC-OCT) is a high-resolution imaging tool that provides real-time, and non-invasive diagnosis. Comparatively, higher diagnostic accuracy of AK was achieved using LC-OCT than conventional techniques. The histopathology of the skin is evaluated based on the estimated atypia

	
Statistical Analysis Plan
 
Sponsor: ALMIRALL, S.A.
 
Protocol number: M-14789-42

---	---

score at cellular level of the LC-OCT images. Atypia score is calculated using certain quantitative and qualitative metrics.

In this study, only one Spanish site will perform LC-OCT: Hospital Clinic de Barcelona.

Each patient will be assessed for 2 lesions (1 clinical lesion and 1 subclinical lesion) at each visit. Information regarding whether assessment is performed or not in the respective patient will be collected in the eCRF with Yes/No responses. Data pertaining to individual cellular metrics of the atypia score and the atypia score will be collected only in the source documents externally and not entered in the eCRF.

Analysis methodology

LC-OCT data of clinical and subclinical lesions at only one selected site, i.e., Hospital Clinic de Barcelona (Site # 101) will be collected at baseline (Day 0; pre-dose), Day 8, Day 15, Day 29, and Day 57 and atypia scores will be calculated on those 3D images externally, i.e., by the site.

Results of this analysis will be presented separately and included in the Clinical Study Report (CSR).

A table summarizing data collected in Line-field Confocal Optical Coherence Tomography (LC-OCT) eCRF page, in terms of number of patients who performed LC-OCT assessment at each timepoint, will be provided.

Patient data listings for LC-OCT population will be provided, reporting the assessment's performance and the related assessment date, for each visit.

Data handling rules

No missing imputation will be performed.

Sensitivity of secondary analysis

Not applicable.

6.3.3. Exploratory efficacy analysis

Not applicable.

6.3.4. Measurement of Treatment Compliance

Medication adherence will be recorded using a self-administered Patient Diary from Day 0 to Day 4. Questions reported in Patient Diary will be related to usage pattern

	
Statistical Analysis Plan
 
Sponsor: ALMIRALL, S.A.
 
Protocol number: M-14789-42

---	---

(dosage, frequency, and site) of study medication application, adverse reactions, and reasons for any missed or delayed doses.

Medication adherence assessed with patient-kept diary will be summarized with frequency distribution from Day 0 to Day 4, reporting the number of patients who applied Tirbanibulin and the number of recorded missing applications (i.e., no missing doses, 1 missing dose, 2 missing doses, 3 missing doses, 4 missing doses or 5 missing doses) at each considered day and overall.

In advance, patients' compliance will be evaluated computing the number and percentage of patients who received all Tirbanibulin doses and the number and percentage of patients who didn't received all ones.

6.4. Safety Evaluation

The safety analysis will be performed on the Safety population.

Adverse events and local tolerability signs during the treatment period will be collected through patient diary and evaluated at each visit or through telephonic follow-up as final safety evaluation.

6.4.1. Extent of Exposure

Exposure to the study treatment will be based on the number of Tirbanibulin applications administered from Day 0 to Day 4 which will be summarised as well as number of missed treatment's applications.

Moreover the proportion of patients who applied all Tirbanibulin doses, and the proportion of patients by number of missed doses will be provided.

6.4.2. Concomitant medications

Concomitant medications are defined as therapies ending or ongoing after the first Tirbanibulin application.

Since no imputation will be performed in case of partial/missing medication's start or end date, the presence of at least one of the following conditions will be used to identify concomitant medication:

- If medication status is ongoing;
- If medication end date is missing and medication status is not ongoing or missing;
- If medication end date is complete, medication status is not ongoing or missing and medication end date \geq Tirbanibulin start date;

	Statistical Analysis Plan Sponsor: ALMIRALL, S.A. Protocol number: M-14789-42
---	--

- If day and month of medication end date are missing, medication status is not ongoing or missing and medication end date year \geq Tirbanibulin start date year;
- If only day of medication end date is missing, medication status is not ongoing or missing and medication end date year $>$ Tirbanibulin start date year;
- If only day of medication end date is missing, medication status is not ongoing or missing, medication end date year = Tirbanibulin start date year and medication end date month \geq Tirbanibulin start date month.

Concomitant medications/therapies and surgical/medical procedures will be described by ATC code (2nd level class) and Preferred Term, presenting the number and percentage of patients taking at least one concomitant medication/procedures.

Moreover, surgical and medical procedures administrated to each patient will be described by System Organ Class and Preferred Term, presenting the number and percentage of patients undergoing at least one surgical or medical procedure.

6.4.3. Adverse Events

Adverse Events (AEs) are defined as any untoward medical occurrence associated with the use of an intervention in humans after providing written informed consent for participation in the study until the end of study visit.

Tables reporting a summary of AEs will be produced including:

- the total number of events and absolute and relative frequencies of patients with AEs;
- the total number of events and absolute and relative frequencies of patients with Serious AEs (SAEs);
- the total number of events and absolute and relative frequencies of patients with AEs related to treatment (i.e., for patients who reported “Relationship to Study Treatment=Related or Possibly Related” in ADVERSE EVENTS eCRF page);
- the total number of events and absolute and relative frequencies of patients with fatal AEs;
- the total number of events and absolute and relative frequencies of patients with AEs leading to treatment discontinuation.

AEs summaries will be presented by SOC, PT and maximum severity using the MedDRA dictionary. All related AEs with study treatment, SAEs, AEs with an outcome of death, AEs leading to treatment discontinuation will be summarized by MedDRA SOC and PT.

	
Statistical Analysis Plan
 
Sponsor: ALMIRALL, S.A.
 
Protocol number: M-14789-42

---	---

If a patient reported more than one AE coded to the same PT, in the analysis the patient will be counted only once in the incidence calculation for that PT. Similarly, if a patient has more than one AE in the same SOC, the patient will be counted only once in the total number of patients with an AE for that SOC.

SAE with fatal and non-fatal outcome will be listed by patient.

All the AEs, SAEs and Adverse Events of Special Interest (AESIs - identified as Basal Cell Carcinoma (BCC), Squamous Cell Carcinoma (SCC) and melanoma and distinguished through the PTs included in Standardised MedDRA Query (SMQ): "Skin neoplasms, malignant and unspecified") will be also listed as well as all reported deaths.

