The **Enrolled population** will consist of all patients who signed the informed consent form.

The **Full analysis set (FAS) population** will consist of all patients who signed the informed consent form and applied at least one dose of tirbanibulin.

The **Evaluable patient population** will consist of FAS patients who complete the 57 days of observation and have the TSQM-9 assessment.

The **Safety patient population** will consist of Full analysis set patients.

The primary and secondary analyses will be done on the Evaluable patient population.

Analyses of Endpoints

Primary Endpoint

The mean or the median for Convenience, Efficacy and Total satisfaction of TSQM-9 at Day 57 will be estimated with the corresponding 95% CI.

Secondary Endpoints

➤ Patient-reported outcomes

- The mean or median change from baseline in total Skindex-16 and its components at Day 57 will be estimated with 95% CI.
- The mean or median of the Likert Scale for organoleptic properties of tirbanibulin at Day 8 will be estimated with 95% CI.
- The mean or median for Convenience, Efficacy, Side Effects and Total satisfaction of TSQM 1.4 at Day 57 will be estimated with 95% CI.
- Treatment preference assessed through question 1 (Q1) to question 9 (Q9) of the EPQ at Day 57 will be summarized with frequency distribution and 95% CI for proportions.

➤ Efficacy

- The percentage of patients with complete (100%) clearance of all lesions within the application area at Day 57 will be estimated with the 95% CI for proportions.
- The percentage of patients with partial clearance, defined as a reduction of at least 75% in the number of lesions within the application area, at Day 57 will be estimated with the 95% CI for proportions.
- The mean or median number of old and new AK lesions at Day 57 will be estimated with corresponding 95% CI.
- Olsen characterization at baseline (Day 0; pre-dose) and Day 57 will be summarized with frequency distribution and 95% CI for proportions.
- RCM and OCT of subclinical lesions (at only one selected site: Hospital Clinic de Barcelona) at baseline (Day 0; pre-dose), Day 8, Day 15, Day 29, and Day 57 will be summarized.

➤ Physician Reported Outcomes

- Physician outcomes assessed at Day 57 through question 1 (Q1) to question 10 (Q10) of EPQ will be summarized with frequency distribution and 95% CI for proportions.

➤ Safety Endpoints

All safety data collected from the study start through the last follow-up visit will be summarized.

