10.6.2 Reporting of Adverse Events

The reported or observed AEs must be recorded on the AE page of the eCRF, and should be described in the following manner:

- The nature of the AE will be described in precise, standard medical terminology (i.e., not necessarily the exact words used by the patient). If known, a specific diagnosis should be recorded instead of listing signs and symptoms (e.g., allergic contact dermatitis).
- The duration of the AE will be described by the start date and end date.
- The location for cutaneous adverse events will be described as at or just around the application area (≤ 2 cm from the application area) or distant (>2 cm from the application area).
- The intensity of the AE will be described in terms of mild, moderate, or severe according to the Investigator's clinical judgment. And assign to 1 of the following categories:
 - Mild – means awareness of symptoms or signs, but easily tolerated (acceptable).

Clinical Trial **M-14789-42**

Clinical Trial Protocol Version No.1.0, Date 08/05/2022

- Moderate – means enough discomfort to interfere with usual activity (disturbing).
- Severe – interferes significantly with ability to do work or usual activity (unacceptable).
- The causal relationship of the event to use of the IMP will be described in terms of:
 - Not related: Event or laboratory test abnormality, definitely not related to trial drug, as related to other drug, chemicals, or underlying disease
 - Unlikely related: Event or laboratory test abnormality, with a time to drug intake that makes a relationship improbable; disease or other drugs, chemicals or underlying disease provide plausible explanations
 - Possibly related: Event or laboratory test abnormality, with a reasonable time relationship to drug intake; could also be explained by underlying disease or other drugs or chemicals; information on drug withdrawal may be lacking or unclear
 - Related: Event or laboratory test abnormality, with a reasonable time relationship to drug intake, unlikely to be attributed to underlying disease or other drugs or chemicals; response to withdrawal clinically reasonable (positive dechallenge)

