‘Possibly related’ and ‘Related’ will be considered as ‘related’ for reporting purposes. If the events are assessed as unlikely related or not related to the suspect IMP, the event does not qualify for reporting purposes. In the absence of information on causality from the reporting Investigator, the CRO will immediately contact the reporting Investigator to request a causality assessment. The case will be updated with the follow-up information and reported accordingly. If no causality is provided by the Investigator, the Sponsor’s assessment will be considered for submission purposes.

- The outcome of the event will be described in terms of:
 - Recovered/resolved
 - Recovering/resolving
 - Recovered/resolved with sequelae
 - Not recovered/not resolved
 - Fatal
 - Unknown
- The action taken on the IMP will be captured as:
 - Drug withdrawn
 - Dose reduced
 - Dose increased
 - Dose not changed
 - Not applicable

AEs will be collected only once with its maximum severity, except when the AE started before first IMP administration, persisted after it and worsened in severity any time after first IMP. In

this latter case, the AE will be collected with each respective severity. AE term recorded must be exactly the same in the different time-points where AE is reported in the eCRF.

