11.4.1 Analysis of Safety and Tolerability Endpoints

The analyses of safety and tolerability outcomes will be performed on the Safety Population. Safety outcomes include adverse events, blood pressure and heart rate (vital signs).

LSRs

LSRs assessment results obtained through Day 57 will be summarized by visit reporting for each of the six signs (erythema, flaking/scaling, crusting, swelling, vesiculation/pustulation, and erosion/ulceration at the application-site) the number and percentage of patients corresponding to each of the score ranging from 0=absent to 3=severe. In addition, a composite score will be calculated as the sum of the scores for all six signs (range 0 to 18, with higher scores indicating more severe reactions) at each visit for each patient and summarized with standard summary statistics for continuous variables.

Application-site reactions such as application-site pruritus or application-site pain (including pain, tenderness, stinging, and burning sensation) not classified as LSRs will be reported as adverse events (AE)..

Adverse Events

The incidence of AEs, SAEs and AESI recorded throughout the study will be summarized by MedDRA SOC and PT. A summary of AEs by SOC, PT and severity will be also provided. All related AEs, SAEs, AEs with an outcome of death, AEs leading to treatment discontinuation will be summarized by MedDRA SOC and PT. Deaths will be listed together with all relevant information.

The frequency of comorbidities will be analyzed descriptively.

Vital Signs

Vital signs (blood pressure and heart rate) will be summarized at each time point and as change from screening value with descriptive statistics.

Medication Adherence

Medication adherence assessed with patient-kept diary will be summarized with frequency distribution from Day 0 to Day 4

11.4.2

Analysis of Pharmacokinetic Parameters

Not applicable

11.4.3

Pharmacokinetic/Pharmacodynamic Analysis

Not applicable

11.5

Handling of Missing Data

In case of missing values, no imputation will be done. Further details on the handling of missing data will be provided in the SAP.

11.6

Multiplicity Strategy

No statistical test will be conducted, so there is no need to consider multiplicity issue.

11.7

Interim Analysis

An intermediate descriptive analysis is planned when 50% of patients have completed the study. Further details will be provided in the SAP.

12 Data Handling, Processing, and Record Keeping

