
To evaluate efficacy outcomes of patients following treatment with Tirbanibulin ointment 1% administered once daily for 5 consecutive days.
	
 • Lesion clearance. • Number of lesions. 
 • Lesion clearance. • Number of lesions. 
 • Total AK lesion count. • New AK lesion count. • Old AK lesion count. 
Olsen characterization.
	
Proportion of patients with complete (100%) clearance of all lesions within the application area with 95% confidence interval.
 
Proportion of patients with partial (>75%) clearance of all lesions within the application area with 95% confidence interval.
 
Number of new and old AK lesions with 95% confidence interval.
 
Proportion of patients by Olsen characterization with 95% confidence interval.

	Statistical Analysis Plan Sponsor: ALMIRALL, S.A. Protocol number: M-14789-42
---	--

OBJECTIVES	VARIABLES	ENDPOINTS

To evaluate safety outcomes of patients following treatment with Tirbanibulin ointment 1% administered once daily for 5 consecutive days.
	
LC-OCT data of clinical and subclinical lesions.
 
 • Adverse events maximum severity grade. • Adverse events SOC. • Adverse events PT. • LTS composite score. • LTS severity grade assessed by physicians. • Number of LTS reported reported by patients. 	
LC-OCT of clinical and subclinical lesions as Atypia scores.
 
Proportion of patients reported at least one adverse event by incidence and severity.
 
Proportion of patients reported at least one local tolerability sign (LTS).

To evaluate medication adherence of patients following treatment with Tirbanibulin ointment 1% administered once daily for 5 consecutive days.
	
Number of missing doses applied.
	
Proportion of patients applying Tirbanibulin doses.

Exploratory objective(s): NA	NA	Exploratory endpoint(s): NA

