4.2. Definitions

Study Phases

The following phases are identifiable:

- **Screening period:** Day -28 to Day -1
Period of up to 4 weeks before Baseline used to assess patient eligibility. The screening period starts with the signing of the informed consent. No re-screening of patients is allowed.
- **Treatment period:** Day 0 (Baseline) to Day 4
This period started with the first treatment administration (Day 0) and ended at the last treatment administration planned at Day 4.
At the Baseline visit (Day 0), after confirmation of eligibility, patients will be included and treated with Tirbanibulin administered topically at a dose of 2.5 mg once daily for 5 consecutive days to a contiguous up to a 25 cm² area field on the face or scalp.
- **Follow-up period:** Day 5 to Day 57
In this period 2 visits are scheduled at Day 8 (Visit 3) and at Day 57 (Visit 4, Final Visit), but only for 1 site (i.e. Hospital Clinic de Barcelona), study visits will be held at Screening and on Day 0 (baseline), Day 8, Day 15, Day 29 and Day 57.

	
Statistical Analysis Plan

	
Sponsor: ALMIRALL, S.A.

	
Protocol number: M-14789-42

- **End of Study**

Day 57 visit (Visit 4) will constitute the End of Study Visit.

Definition of Screening Failures

Participants who sign an informed consent form and subsequently found to be ineligible (i.e., due to non-meeting of inclusion/exclusion criteria) will be considered screen failures. The reason for screen failure (i.e., protocol deviation and non-protocol deviation) will be properly summarized.

Definition of Baseline

Baseline date (Day 0) is defined as the date of the first Tirbanibulin administration, i.e., Visit 2 date.

First/Last Administration of Study Treatment

The date of first treatment administration is the first “Date of study medication application” in TIRBANIBULIN (STUDY DRUG) APPLICATION eCRF page (and it should coincide with Baseline date).

The date of last treatment administration is the “Last known date subject took study treatment” in END OF TREATMENT DISPOSITION eCRF page.

End of Trial

The “end of trial” is defined as the date when all patients complete the Day 57 visit or prematurely discontinue from the study, i.e., “Date of Discontinuation /Study completion” date in END OF STUDY DISPOSITION eCRF page.

Completed Patient

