5. ANALYSIS POPULATIONS

Starting from Screened patients (i.e., all patients who signed the informed consent form), the following analysis populations will be defined for statistical analysis:

- **Enrolled population:** all patients who signed the informed consent form and completed the screening disposition.
- **Full analysis set (FAS) population:** all patients who signed the informed consent form and applied at least one dose of Tirbanibulin.
- **Evaluable patient population:** FAS patients who completed the 57 days of observation and have the TSQM-9 assessment.
- **Safety patient population:** Full analysis set patients.
- **LC-OCT Population:** FAS patients who performed at least one valid LC-OCT assessment (i.e., FAS patients enrolled at site 101).

	Statistical Analysis Plan Sponsor: ALMIRALL, S.A. Protocol number: M-14789-42
---	--

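### SAP 6.4.3 has no treatment-emergent rule, so pre-dose events of dosed patients enter the all-AE, SAE and SOC/PT/maximum-severity tables; treatment-emergent tables should be added

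*SAP*

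**What the plan says.** The safety objective in SAP 2 begins "To evaluate safety outcomes of patients following treatment with Tirbanibulin ointment 1". SAP 6.4.3 then defines the events to be counted: "Adverse Events (AEs) are defined as any untoward medical occurrence associated with the use of an intervention in humans after providing written informed consent", up to the end-of-study visit. It lists summary tables for all AEs, SAEs, related AEs, fatal AEs and AEs leading to treatment discontinuation. It also lists tables of all AEs by SOC, PT and maximum severity.

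SAP 6.4 runs these on the Safety population. SAP 5 equates that with the full analysis set: "all patients who signed the informed consent form and applied at least one dose of Tirbanibulin". SAP 4.2 describes screening, which starts at consent, as "Period of up to 4 weeks before Baseline used to assess patient eligibility".

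The protocol sets the same scope. Its synopsis says "All safety data collected from the study start through the last follow-up visit will be summarized". Protocol 11.4.1 says "The incidence of AEs, SAEs and AESI recorded throughout the study will be summarized by MedDRA SOC and PT".

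**The concern.** Nothing in SAP 6.4.3, the definitions in 4.2 or the populations in 5 separates an event that began before the first application from one that began after it. Requiring at least one dose removes screen failures, but it keeps the earlier events of everyone who went on to be dosed.

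The study has one arm and no control, so a reader will tend to take the overall AE and SAE percentages as experience after tirbanibulin. As planned, they also cover an untreated interval whose length differs between patients.

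**Working it through.** **Can pre-dose events reach the database?** Yes, by the rules in protocol version 1.0.
- Protocol 10.6.3 collects AEs from signature of consent, and treats abnormalities in screening or baseline tests as AEs if a trial procedure is thought to have caused them.
- Both schedules (protocol Table 1 and SAP 3.4) mark AE recording on Day 0 with the footnote for procedures done before application.
- Protocol 10.6.2 provides for an AE that starts before the first dose and worsens after it: in "this latter case, the AE will be collected with each respective severity".

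**Which tables are affected?**
- All-AE, SAE and SOC/PT/maximum-severity tables: affected, since nothing filters on onset.
- Related AEs: essentially not, because relatedness presupposes drug intake.
- AEs leading to treatment discontinuation: essentially not, because treatment must have started.
- Fatal AEs: essentially not, because a death in a dosed patient comes after dosing.
- Total number of events: a worsened AE recorded at each severity can count twice. Patient counts within a PT or SOC are de-duplicated by SAP 6.4.3.
- AEs of special interest (AESIs): the SAP picks these by PT alone. Protocol 10.6.6 limits them to Days 0 to 57, and 10.6.6.1 to skin cancers within the treatment area.

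**Can the split be made?** Largely. Protocol 10.6.2 states "The duration of the AE will be described by the start date and end date". The documents show no flag for before or after dosing on Day 0, so some Day 0 events cannot be placed.

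**How large could the effect be?** The plan gives no AE rate for this study and no figure to reproduce, so this is an illustration. Let p be the incidence over Day 0 to Day 57 (58 days), s the days from consent to first dose, and f the share of pre-dose events captured. With a constant background rate, and ignoring the visit windows of ±3 days:

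incidence from consent = 1 − (1 − p)^((f·s + 58)/58)

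For p = 0.10, f = 1:
- s = 7: 1 − 0.90^(65/58) = 0.1114
- s = 28: 1 − 0.90^(86/58) = 0.1446

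| Assumption | s = 1 | s = 7 | s = 14 | s = 28 |
|---|---|---|---|---|
| p = 10%, all captured | 10.2% | 11.1% | 12.3% | 14.5% |
| p = 10%, half captured | 10.1% | 10.6% | 11.1% | 12.3% |
| p = 5%, all captured | 5.1% | 5.6% | 6.2% | 7.3% |

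If all 420 planned patients were dosed, the first row means 46.8 patients at s = 7 and 60.7 at s = 28, against 420 × 0.10 = 42. The share of observation time before dosing is 7/65 = 10.8% and 28/86 = 32.6%.

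**The case against.** The strongest answer is that the SAP does what the protocol asks. The synopsis and protocol 11.4.1 both call for safety data from the whole study, and the endpoint is simply the incidence and severity of AEs. The phrase about outcomes following treatment is repeated for every objective. This stands. A reader might infer that the SAP departs from the protocol, or that the all-AE tables are wrong and should be replaced. The documents support neither: the all-AE tables are required, and a count plus a listing of pre-dose events would not meet the SOC/PT summary in 11.4.1.

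A reader might also point to the SAP's split of medications at first application (6.2, 6.4.2) as proof that first dose is the plan's boundary. It is only partial support, because protocol 9.6.2 defines concomitant therapy from consent.

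The effect may also be small, and this stands too. No AE assessment is marked at Screening, the diary starts on Day 0, and known prior conditions are not AEs. Few screening procedures (history, examination, vital signs, lesion count, pregnancy test) could cause an AE. Patients with a notable event during screening may never be dosed, which takes them out of the Safety population. The constant-rate figures ignore that selection.

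Finally, all analyses are descriptive, no comparison with the earlier tirbanibulin studies is planned, and all AEs are listed. That limits the harm, but a listing does not supply an incidence after treatment.

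**Conclusion.** The point holds as a modest, inexpensive improvement. Followed exactly, the plan mixes pre-dose with post-dose events in the all-AE, SAE and SOC/PT/maximum-severity tables, and offers no overall AE or SAE table limited to the period after first application.

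It does not follow that the reported rates will be materially inflated; the documents do not give the information needed to say so. The 11.1% to 14.5% range (7 to 28 days of screening) rests on an assumed 10% incidence, a constant rate and full capture, and is an upper bound under those assumptions. With very short screening the effect is negligible.

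The missing onset rule is in the SAP itself. The AE collection and AESI rules cited are from protocol version 1.0, whereas SAP 1 refers to versions 3.0 (Spain) and 2.0 (Italy). They should be checked there.

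**What to change.** In SAP 6.4.3:
- Define a treatment-emergent AE as one that starts, or worsens in severity, on or after the first application.
- Treat Day 0 and partial-date onsets as emergent unless the record shows that they were pre-dose. This classifies events without imputing dates, so it is compatible with SAP 4.4.1.
- Count a worsened AE once in the treatment-emergent tables, at its worsened severity.
- Add treatment-emergent AE, SAE and SOC/PT/maximum-severity tables, and base statements about safety after treatment on them.
- Keep the all-AE SOC/PT tables required by protocol 11.4.1, and show pre-dose AEs in a separate listing.
- Flag AESIs by the protocol's limits: Days 0 to 57 and within the treatment area.

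The cost is SAP wording and some extra programming; no new data are needed. Day 0 events that cannot be placed stay emergent, which slightly overstates the emergent count. SAP 6.6 reports that an interim analysis has already been run. The new tables will not match the interim ones, so any interim-to-final comparison should use the retained all-AE tables.
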